10.2 Patient demographics/other baseline characteristics

Demographic and other baseline data including disease characteristics will be listed and summarized descriptively by treatment group for the FAS or the Safety Set.

Categorical data will be presented as frequencies and percentages. For continuous data, mean, standard deviation, median, minimum, and maximum will be presented.

[figure not shown]
Relevant medical histories and current medical conditions at baseline will be summarized separately by system organ class and preferred term, by treatment group.

10.3 Treatments (study treatment, concomitant therapies, compliance)

The Safety set will be used for the analyses below.

Categorical data will be summarized as frequencies and percentages. For continuous data, mean, standard deviation, median, 25th and 75th percentiles, minimum, and maximum will be presented.

The duration of exposure in days to asciminib and bosutinib, as well as the dose intensity (computed as the ratio of actual cumulative dose received and actual duration of exposure) and

the relative dose intensity (computed as the ratio of dose intensity and planned dose intensity) will be summarized by means of descriptive statistics.

The number of patients with dose adjustments (reductions, interruption, or permanent discontinuation) and the reasons will be summarized by treatment group and all dosing data will be listed.

Concomitant medications and significant non-drug therapies prior to and after the start of the study treatment will be listed and summarized according to the Anatomical Therapeutic Chemical (ATC) classification system, by treatment group.

10.4 Primary objective

The primary objective of the study is to evaluate the efficacy of asciminib at the recommended dose in CML patients in chronic phase, previously treated with 2 or more tyrosine kinase inhibitors and to compare this efficacy profile in this population with that achieved by patients receiving bosutinib.

10.4.1 Variable

The primary efficacy variable of the study is the Major Molecular Response (MMR) rate at 24 weeks. A patient will be counted as having achieved MMR at 24 weeks if he meets the MMR criteria (BCR-ABL1 ratio $\leq 0.1\%$) at 24 weeks.

10.4.2 Statistical hypothesis, model, and method of analysis

The MMR rate at 24 weeks will be calculated based on the FAS and according to the Intention-To-Treat (ITT) principle. MMR rate and its 95% confidence interval based on the Pearson-Clopper method will be presented by treatment group. The confidence interval for the difference in MMR rate between treatment groups will be provided using the Wald method.

The null hypothesis is that there is no difference between the treatment groups with respect to MMR rate at 24 weeks. The Cochran-Mantel-Haenszel chi-square test, stratified by the randomization stratification factor, i.e. major cytogenetic response status (PCyR or CCyR vs. others) at screening, will be used to compare MMR rate between the two treatment groups, at the two-sided 5% level of significance. The Mantel-Haenszel estimate of the common risk difference and the corresponding 95% confidence interval will also be provided.

10.4.3 Handling of missing values/censoring/discontinuations

Only patients with MMR at 24 week visit are considered responders. In other words, any patient who achieves MMR before 24 weeks, but is no longer in MMR at 24 weeks, will be considered as a non-responder in this primary analysis. Patients discontinuing the randomized treatment (having performed an EOT visit) prior to 24 weeks due to any reason will be considered as non-responders. One exception to the rule above is if the 24-week PCR evaluation is missing, but both a PCR evaluation at 16 weeks and a PCR evaluation at 36 weeks indicate MMR, the 24-week assessment is imputed as a 'Response'. If PCR evaluations are performed at unscheduled visits closer to the Week 24 visit (before or after), these will be taken into account for the imputation.

10.4.4 Supportive and Sensitivity analyses

The analysis of the primary endpoint will also be repeated on the PPS if the PPS is different from the FAS.

Subgroup analyses and a logistic regression analysis will be employed. Refer to the exploratory objectives [Section 10.6.1](#) for further details.

10.5 Secondary objectives

The secondary objectives in this study are as follows:

- To compare additional parameters of the efficacy of asciminib versus bosutinib, defined as:

Key secondary endpoints

[figure not shown]
- MMR rate at 96 weeks

Other efficacy endpoints

- Cytogenetic response (Complete, Partial, Major, Minor, Minimal, no response) rate at all scheduled data collection time points including, 24, 48 and 96 weeks.
- Cytogenetic response (Complete, Partial, Major, Minor, Minimal, no response) rate by all scheduled data collection time points including, 24, 48 and 96 weeks.
- MMR rate at all scheduled data collection time points (except 24 and 96 weeks which are already covered by primary and key secondary endpoints)
- MMR rate by all scheduled data collection time points including 24, 48 and 96 weeks.
- Time to MMR
- Duration of MMR
- Time to CCyR
- Duration of CCyR
- Time to treatment failure
- Progression free survival
- Overall survival
- To compare the safety and tolerability profile of asciminib versus bosutinib
- To characterize the PK of asciminib in the CML-CP population

10.5.1 Key secondary objective(s)

The key secondary endpoint to be evaluated is MMR rate at 96 weeks, which is defined as the proportion of patients with MMR at 96 weeks and derived in a similar fashion to MMR rate at 24 weeks.

10.5.1.1 Analysis for key secondary objectives

The null hypothesis is that there is no difference between the treatment groups with respect to MMR rate at 96 weeks. Formal statistical testing of the key secondary endpoint will be performed with $\alpha = 0.05$ (two-sided) only if the primary endpoint (i.e. MMR rate at 24 weeks) is significant by means of a gatekeeping procedure to control the overall alpha level. Otherwise, no statistical testing will be performed, and any analysis will be considered exploratory.

MMR rate at 96 weeks will be evaluated in a similar fashion to the primary analysis of MMR rate at 24 weeks. The rate and the associated 95% confidence interval based on the Pearson-Clopper method will be presented by treatment group. Confidence interval for the difference between treatment groups will be provided using the Wald method.

Statistical testing will be performed via CMH chi-square test stratified by the randomization strata. The Mantel-Haenszel estimate of the common risk difference and the corresponding 95% confidence interval will also be provided.

If the PCR evaluation at 96 weeks is missing, but a PCR evaluation both at 84 weeks and 108 weeks indicate MMR, the 96 week assessment is imputed as a “response”, assuming that MMR is maintained between 84 and 108 weeks. If PCR evaluations are performed at unscheduled visits closer to the Week 96 visit (before or after), these will be taken into account for the imputation.

10.5.2 Other secondary efficacy objectives

Unless otherwise stated the FAS will be used for the analysis of all other secondary efficacy endpoints. The exceptions are using the Molecular Responder Set for duration of MMR and time to MMR, the CCyR Analysis Set for CCyR rates, and the Cytogenetic Responder Set for duration of CCyR and time to CCyR.

No statistical testing of non-key secondary efficacy endpoints will be performed, and any analysis will be considered exploratory.

[figure not shown]
Molecular Response

MMR rates at scheduled time points (except 24 and 96 weeks which have been specified as primary and key secondary endpoints) will be evaluated in a similar fashion to the primary analysis of MMR rate at 24 weeks. Patients discontinuing the randomized treatment prior to a specific time point due to any reason will be considered as non-responders for that time point.

MMR rates by scheduled time points are defined as the proportion of patients who achieve MMR at or before the specified visit, i.e. if a patient achieves an MMR but then loses it before or at the visit, he/she will still be classed as achieving MMR by that time point.

For each endpoint the rate and the associated 95% confidence interval based on the Pearson-Clopper method will be presented by treatment group. Confidence intervals for the differences in any response rates between treatment groups will be provided using the Wald method.

Statistical testing will be performed via CMH chi-square tests stratified by the randomization strata. The Mantel-Haenszel estimate of the common risk difference and the corresponding 95% confidence interval will also be provided.

Duration of MMR is defined in [Section 7.2.1.1](#) as the time between the date of the first documented MMR and the earliest date of loss of MMR, progression to AP/BC, or CML-related death for patients in the Molecular Responder Set. The time will be censored at the last molecular assessment (PCR) date while on treatment for patients who have not experienced any of the above events.

Duration of MMR will be analyzed by K-M method and presented by K-M plots. The estimated rates of patients who are still responding at various time points will also be provided using K-M method.

The cumulative incidence of MMR will be graphically displayed by an increasing step function. This curve will increase each time (after randomization) at which a new responder is observed and thus will increase up to the best observed response rate (e.g. up to 50% if half of the patients in the analysis population are able to achieve response).

Time to MMR is defined in [Section 7.2.1.1](#) and calculated as: date of first MMR - date of randomization +1, for patients in the Molecular Responder Set. Descriptive statistics (minimum, maximum, median, quartiles, mean, sd) of time to MMR will be provided for the two treatment groups separately.

Cytogenetic Response

Patients in FAS will be categorized with counts and percentages provided for cytogenetic response (Complete, Partial, Major, Minor, Minimal, No Response) at and by (i.e. best response up to a specified time point) scheduled time points. Shift tables will also be employed to examine the changes in cytogenetic response category from baseline.

Since there are expected to be only limited numbers who are actually in CCyR at baseline the analysis of CCyR rate at and by scheduled time points will only include patients who are not in CCyR at baseline, i.e. the CCyR Analysis Set.

CCyR rates at and by scheduled time points etc. and the associated 95% confidence intervals based on the Pearson-Clopper method will be presented by treatment group with the analysis of these endpoints only including patients who are not in CCyR at baseline.

Confidence intervals for the differences in any response rates between treatment groups will be provided using the Wald method.

Statistical testing will be performed via CMH chi-square tests stratified by the randomization strata. The Mantel-Haenszel estimate of the common risk difference and the corresponding 95% confidence interval will also be provided.

Time to CCyR is defined for patients in the Cytogenetic Responder Set as: date of first CCyR - date of randomization +1. Descriptive statistics (minimum, maximum, median, quartiles, mean, sd) of time to CCyR will be provided for the two treatment groups separately.

The cumulative incidence of CCyR will also be graphically displayed by an increasing step function. This curve will increase each time (after randomization) at which a new responder is observed and thus will increase up to the best observed response rate.

Duration of CCyR is defined as the time between date of first documented CCyR and the earliest date of loss of CCyR, progression to AP/BC, or CML-related death for patients in the

Cytogenetic Responder Set. The time will be censored at the last cytogenetic assessment date on treatment for patients for whom none of the above events is reported or last PCR evaluation on treatment indicating MMR.

Duration of CCyR response will be analyzed by K-M method and presented by K-M plots. The estimated rates of patients who are still responding at various time points will also be provided using K-M method.

Treatment failure, disease progression and survival

Time to treatment failure (TTF) is defined as the time from date of randomization to an event of treatment failure. The following events will constitute ‘treatment failure’, and are based on the ELN criteria ([Baccarani et al 2013](#)) defining failure of a second line treatment adapted to include discontinuation of randomized treatment as an event:

- No CHR or > 95% Ph+ metaphases at three months after randomization or thereafter
- BCR-ABL1 ratio > 10% IS and/or > 65% Ph+ metaphases at six months after randomization or thereafter
- BCR-ABL1 ratio > 10% IS and/or > 35% Ph+ metaphases at 12 months after randomization or thereafter
- Loss of CHR, CCyR or PCyR at any time after randomization
- Detection of new BCR-ABL1 mutations which potentially cause resistance to study treatment at any time after randomization
- Confirmed loss of MMR
- New clonal chromosome abnormalities in Ph+ cells: CCA/Ph+: at any time after randomization
- Discontinuation from randomized treatment for any reason

For patients who have not reached treatment failure, their TTFs will be censored at the time of last study assessment (PCR, cytogenetic, hematologic or extramedullary) before the cut-off date.

Progression-Free-Survival (PFS) is defined as the time from the date of randomization to the earliest occurrence of documented disease progression to AP/BC or the date of death from any cause (including progressions and deaths observed during the survival follow-up period) before the cut-off date.

The time will be censored at the date of last study assessment (PCR, cytogenetic, hematologic or extramedullary) or last post-treatment follow-up for patients without event.

Overall survival (OS) is defined as the time from the date of randomization to the date of death (including the survival follow-up period). Patients who are alive at the time of the analysis data cutoff date will be censored at the date of last contact before the cut-off date.

TTF, PFS and OS will be estimated and graphically displayed using the K-M approach on FAS. The estimated rates by K-M method at various time points will be provided and the endpoints will be compared between the two treatment groups using stratified log-rank test stratified by the randomization strata. The hazard ratio and 95% confidence intervals will be computed from a stratified Cox model.

10.5.3 Safety objectives

10.5.3.1 Analysis set and grouping for the analyses

For all safety analyses, the safety set will be used. All listings and tables will be presented by treatment group.

The overall observation period will be divided into three mutually exclusive segments:

1. pre-treatment period: from day of subject's first informed consent to the day before first administration of study treatment
2. on-treatment period: from day of first administration of study treatment to 30 days after last actual administration of the same study treatment (including start and stop date)
3. post-treatment period: starting at day 31 after last administration of any study treatment

Summary tables for safety data will be presented for the on-treatment period. Comparative analysis will be performed only for the on-treatment period. Listings of safety data will include pre-treatment, on-treatment, and post-treatment periods, with a flag to indicate data collected before or after the on-treatment period.

The same analysis will be done for patients that switch to asciminib after treatment failure on bosutinib. However, safety events that initiated on or after start of asciminib during the switch treatment phase will be included.

10.5.3.2 Adverse events (AEs)

Summary tables for adverse events (AEs) will include only AEs that started or worsened during the on-treatment period, the *treatment-emergent* AEs.

The incidence of treatment-emergent adverse events (new or worsening from baseline) will be summarized by system organ class and/or preferred term, severity (based on CTCAE grades), type of adverse event, relation to study treatment.

Serious adverse events, non-serious adverse events and adverse events of special interest (AESI) during the on-treatment period will be tabulated.

[figure not shown]
All deaths (on-treatment and post-treatment) will be summarized.

All AEs, deaths and serious adverse events (including those from the pre-treatment, on-treatment and post-treatment periods) will be listed and those collected before or after the on-treatment period will be flagged.

10.5.3.3 Laboratory abnormalities

Grading of laboratory values will be assigned programmatically as per NCI Common Terminology Criteria for Adverse Events (CTCAE) version 4.03. The calculation of CTCAE grades will be based on the observed laboratory values only, clinical assessments will not be taken into account.

CTCAE Grade 0 will be assigned for all non-missing values not graded as 1 or higher. Grade 5 will not be used.

For laboratory tests where grades are not defined by CTCAE v4.03, results will be categorized as low/normal/high based on laboratory normal ranges.

The following listings and summaries will be generated separately for hematology, and biochemistry tests:

- Listing of all laboratory data with values flagged to show the corresponding CTCAE v4.03 grades if applicable and the classifications relative to the laboratory normal ranges

For laboratory tests where grades are defined by CTCAE v4.03

- Worst post-baseline CTCAE grade (regardless of the baseline status). Each patient will be counted only once for the worst grade observed post-baseline in the on-treatment period.
- Shift tables using CTCAE grades to compare respective baseline to the worst on-treatment value

For laboratory tests where grades are not defined by CTCAE v4.03,

- Shift tables using the low/normal/high/ (low and high) classification to compare respective baseline to the worst on-treatment value.

10.5.3.4 Other safety data

ECG

ECGs (12-lead) including PR, QRS, QT, QTcF, and HR intervals will be obtained for each subject during the study. ECG data will be read and interpreted centrally.

Categorical analysis of QT/QTc interval data based on the number of patients meeting or exceeding predefined limits in terms of absolute QT/QTc intervals or changes from baseline will be presented. In addition, a listing of these patients will be produced by treatment group.

Vital signs

Data on vital signs will be tabulated and listed, notable values will be flagged.

10.5.3.5 Supportive analyses for secondary objectives

Not applicable.

[figure not shown]
10.5.3.6 Tolerability

Tolerability of each study treatment will be assessed by summarizing the number of subjects with dose interruptions and dose reductions. Reasons for dose interruptions and dose reductions will be listed by subject and summarized.

10.5.4 Secondary PK objectives

The PK objective is to characterize the PK of asciminib in CML population.

Using PAS, summary statistics (n, mean, SD, coefficient of variation (CV) for mean, geometric mean, CV for geometric mean, median, minimum and maximum) will be presented for plasma concentration at each scheduled time point. The geometric mean with mean (SD) and individual plasma concentration versus time profiles of asciminib will be displayed graphically.

Using Safety set, concentration data will be listed. Concentration values below the limit of quantification (BLQ) will be set to zero by the Bioanalyst and displayed in listings as zero with a flag. BLQ values will be handled as zero in any calculations of summary statistics, but handled as missing for the calculation of the geometric means and CVs.

Pharmacokinetic parameters will be determined by non-compartmental method(s) using the pharmacokinetic profile of asciminib in patients with full PK sampling. PK parameters listed in [Table 10-1](#) will be derived and reported, when feasible.

Population PK modeling may be performed and the results may be reported in a separate population PK report. Data from this study may be combined with data from other studies for this analysis.

Table 10-1 Non compartmental pharmacokinetic parameters in full PK group

AUC0-12h	The area under the plasma concentration-time curve from time zero to 12 h (mass x time x volume-1) ^a
Cmax	The maximum (peak) observed plasma drug concentration after dose administration (mass x volume-1)
Tmax	The time to reach maximum (peak) plasma drug concentration after dose administration (time)
CL/F	The total body clearance of drug from the plasma after oral administration (volume x time-1)

[figure not shown]
10.6 Exploratory objectives

10.6.1 Exploratory efficacy objectives

- To evaluate the influence of factors such as major cytogenetic status at baseline, failure/intolerance to prior TKIs, line of therapy, gender, race and age on the effect of asciminib with respect to the primary efficacy endpoint.
- To characterize mutations in the BCR-ABL1 gene at Week 1 Day 1, upon confirmed loss of molecular response and/or at end of treatment and examine their association with molecular and cytogenetic response for asciminib vs. bosutinib.
- To assess the efficacy of asciminib when administered as treatment after bosutinib failure according to the 2013 ELN Guidelines.

10.6.1.1 Data analysis of exploratory efficacy objectives

Subgroup analyses will be performed to evaluate the influence of factors such as baseline major cytogenetic response status, baseline/Week 1 Day 1 BCR-ABL1 ATP-binding site mutation status (from local historical record and from Sanger Sequencing), failure/intolerance to prior TKIs, line of therapy, gender, race and age on the primary efficacy endpoint. In addition, a logistic regression analysis will incorporate the key baseline variables into the model to further evaluate the impact of these variables on the primary endpoint and to provide a treatment effect estimate which is adjusted for imbalances in the treatment groups. An adjusted odds ratio for the treatment effect with associated 95% confidence intervals will be presented. Mantel-Haenszel estimates of the common odds ratio and the corresponding 95% confidence interval will also be provided. The effect of asciminib when administered as treatment after bosutinib failure will be assessed using the Switch Analysis Set to estimate response rates (cytogenetic and molecular response) at all scheduled time points after switch, as well as time-to and duration

of response. The analysis of time-to-event endpoints will be conducted only if at least 5 events are observed.

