- At any time after the initiation of therapy, loss of CHR, CCyR or PCyR.
- At any time after the initiation of therapy, detection of new BCR-ABL1 mutations which potentially cause resistance to study treatment (asciminib or bosutinib).
- At any time after the initiation of therapy, confirmed loss of MMR in 2 consecutive tests.
- At any time after the initiation of therapy, new clonal chromosome abnormalities in Ph+ cells: CCA/Ph+.

Conditions preventing patients to switch to asciminib

- Any Grade 3 or 4 toxicity which has not resolved to Grade 2 or lower within 28 days and before starting asciminib treatment.
- Asymptomatic (Grade 2) pancreatitis if not resolved within 28 days
- Disease progression while on bosutinib treatment. The following events are considered disease progression:
 - Accelerated phase (AP) as defined by any of the following:
 - $\geq 15\%$ blasts in the peripheral blood or bone marrow aspirate, but $< 30\%$ blasts in both the peripheral blood and bone marrow aspirate.
 - $\geq 30\%$ blasts plus promyelocytes in peripheral blood or bone marrow aspirate.
 - $\geq 20\%$ basophils in the peripheral blood.
 - Thrombocytopenia ($< 100 \times 10^9/L$) that is unrelated to therapy.
 - Blast crisis (BC) as defined by any of the following:
 - $\geq 30\%$ blasts in peripheral blood or bone marrow aspirate
 - Appearance of extramedullary involvement other than hepatosplenomegaly proven by biopsy (i.e. chloroma).
- QTcF at time of switch > 480 msec or inability to determine QTc interval

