7.2.1.2 Bone marrow analysis and cytogenetics

Cytogenetic response will be assessed locally as the percentage of Ph+ metaphases in the bone marrow and is defined as the following (a review of a minimum of 20 metaphases is required):

- Complete (CCyR) - 0% Ph+ metaphases
- Partial (PCyR) - >0 to 35% Ph+ metaphases
- Major (MCyR) - 0 to 35% Ph+ metaphases
- Minor (mCyR) - >35 to 65% Ph+ metaphases
- Minimal - >65 to 95% Ph+ metaphases
- None - >95 to 100% Ph+ metaphases.

Bone marrow aspirate for cytogenetic analyses will be performed at screening/baseline (performed up to 56 days prior to Week 1 Day 1), at Week 24/S-Week 24, 48/S-48, 72/S-72, 96/S-96 as long as patient has not achieved MMR and at end of treatment (S-end of treatment as specified in [Table 7-1](#) and [Table 7-2](#). For patients on the bosutinib arm an unscheduled bone marrow assessment at week 12 may be performed to evaluate cytogenetic response in consideration for potential dose escalation.

Quantification of the percentage of Ph+ chromosome metaphases, number of metaphases, number positive for Ph chromosome, additional chromosomal abnormalities as well as data from cytologic evaluation (microscopic analysis) of percentage of blasts and promyelocytes will be recorded on the Bone Marrow eCRF. These exams will be performed and analyzed locally. Fluorescent In-situ hybridization (FISH) analysis will not be accepted.

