10.1.6 Other analysis set

For duration of MMR and time to MMR, the MMR Responder Set that will be used is a subset of FAS and includes patients who achieve MMR at any time.

For CCyR rates at and by scheduled time points, the CCyR Analysis Set that will be used is a subset of FAS and includes patients who are not in CCyR at baseline.

For duration of CCyR and time to CCyR, the Cytogenetic Responder Set that will be used is a subset of FAS and includes patients who do not have CCyR at baseline and achieve CCyR at any time on study treatment.

Patients who will receive at least one dose of asciminib after bosutinib failure will form the Switch Analysis Set which will be used for safety and exploratory efficacy endpoints defined on these patients.

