To assess clonal evolution during treatment with asciminib vs. bosutinib	Low level BCR-ABL1 mutation profiles assessed by mass spectrometry at Week 1 Day 1, upon confirmed loss of MMR and/or at EOT. Clonal evolution of several genes implicated in CML assessed by Next Generation Sequencing (NGS) methods	
[REDACTED]	[REDACTED]	
To compare the impact of treatment on patient reported outcomes (PRO) including CML-specific symptoms, patient quality of life, and impact on work productivity and activity impairment from baseline and EOT between treatment arms in all patients	Change in symptom burden and interference from baseline over time according to the MDASI-CML PRO instrument Change in patient's impression of CML symptoms according to Patient Global Impression of Change (PGIC) Change in health utility from baseline over time according to EQ-5D-5L Change in work productivity and activity impairment over time according to WPAI	
To compare the impact of treatment on health care resource utilization between treatment arms in all patients	Health care resource burden over time	
To assess the efficacy of asciminib when administered as treatment after bosutinib failure according to the 2013 ELN Guidelines	
 • Cytogenetic response rate (Complete, Partial, Major, Minor, Minimal, no response) at and by all scheduled data collection time points • MMR rate at and by all scheduled data collection time points 	Refer to Section 10.6

Objective	Endpoint	Analysis
	
• Time to MMR• Duration of MMR• Time to CCyR• Duration of CCyR• Time to treatment failure	

4 Study design

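### Post-switch CCyR is estimated on all switchers, so a patient already in CCyR when leaving bosutinib can be counted as an asciminib responder

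*Combined protocol and SAP*

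**What the plan says.** Section 10.6.1.1 states that asciminib in patients who failed bosutinib "will be assessed using the Switch Analysis Set to estimate response rates (cytogenetic and molecular response) at all scheduled time points after switch", together with time to response and duration of response. Time-to-event endpoints are analysed only if at least 5 events are seen. Section 10.1.6 defines the set: "Patients who will receive at least one dose of asciminib after bosutinib failure will form the Switch Analysis Set". It sets no condition on cytogenetic status at the switch. For these patients Table 3-1 lists "Cytogenetic response rate (Complete, Partial, Major, Minor, Minimal, no response) at and by all scheduled data collection time points", and also time to CCyR and duration of CCyR.

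The randomised arms are handled differently. For CCyR rates, section 10.1.6 says that "the CCyR Analysis Set that will be used is a subset of FAS and includes patients who are not in CCyR at baseline". The Cytogenetic Responder Set, used for time to and duration of CCyR, carries the same exclusion. Section 10.5.2 also tabulates all cytogenetic categories on the whole FAS and adds shift tables from baseline.

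Under section 7.1.2.2, meeting any one failure criterion is enough to switch. One criterion is "At any time after the initiation of therapy, confirmed loss of MMR in 2 consecutive tests". Another is detection of a new BCR-ABL1 mutation that may cause resistance.

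**The concern.** The objective is to learn what asciminib does after bosutinib has failed. A CCyR reached on bosutinib and still present at the switch is not evidence of that, yet the plan as written counts it once it is seen again after the switch. The sponsor took care of this problem for the randomised arms by leaving out patients in CCyR at baseline. No counterpart at the switch appears in the text available.

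The existing CCyR Analysis Set would not solve it if carried over. It is tied to the study baseline, so a patient who was not in CCyR at entry, reached it on bosutinib and kept it would remain in the set.

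What is at stake is the interpretation of one descriptive rate in what is likely to be a small group, where a single patient can move the figure visibly.

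**Working it through.** **Can a patient switch while in CCyR?**

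- CCyR is 0% Ph+ metaphases (7.2.1.2). Loss of MMR is a molecular event: a rise above 0.1% IS with at least a five-fold increase from the lowest value (7.2.1.1). No cytogenetic condition is attached.
- Section 7.2.1.1 lists loss of CCyR as a separate event that may or may not accompany loss of MMR. The protocol itself treats the two as distinct.
- Treatment failure requires bosutinib to stop (7.1.6), so a patient with confirmed loss of MMR and an intact CCyR must leave bosutinib and may switch.
- A new mutation is a second route, though a narrow one. Sanger sequencing is done at Week 1 Day 1, on confirmed loss of MMR and/or at end of treatment, and every 12 weeks only if the first test was positive.

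**When would the carried-over CCyR be counted?** The first scheduled post-switch marrow is S-Week 24 (Table 7-2). If CCyR is still present then, the patient is a CCyR responder in the Switch Analysis Set.

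**Plan's own figures.** The plan gives no number for this analysis. Its only sample size, 222 for the primary endpoint, reproduces: 15% against 35%, two-sided 5%, 90% power, 2:1, pooled variance and no continuity correction give 74 + 148 = 222, with power 90.3%. Nothing in this point changes it.

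**Effect on the rate.** Let N be the number of switchers, k the number in CCyR at the switch who keep it to S-Week 24, and p the CCyR rate in the other N − k.

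- Rate with the k patients included: (k + (N − k)p) / N
- Rate with them excluded: p
- Difference: k(1 − p) / N, so (1 − p) / N per patient

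N, k and p are all assumptions. The only count in the documents is 4 potential candidates by 15-Oct-2018 (Amendment 3 rationale). The planned bosutinib arm of 74 is the ceiling on N at the planned size.

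Points added by one retained case:

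| N | p = 0% | p = 20% | p = 50% |
|---|---|---|---|
| 10 | 10.0 | 8.0 | 5.0 |
| 20 | 5.0 | 4.0 | 2.5 |
| 30 | 3.3 | 2.7 | 1.7 |
| 40 | 2.5 | 2.0 | 1.25 |

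In whole patients with N = 20 and k = 1: 4/19 = 21.1% excluded, against 5/20 = 25.0% included, a difference of 3.9 points.

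**If CCyR is not kept.** A patient in CCyR at the switch who has lost it by the visit lowers the rate at that visit by p/N. With N = 20 and p = 20% this is 0.20/20 = 1.0 point. The upward effect therefore depends on retention. If each such patient has a chance r of still being in CCyR, the average change is (r − p)/N. With r = 70%, p = 20% and N = 20 it is 0.50/20 = 2.5 points.

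**The case against.** The strongest reply has four parts.

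- **The category table is consistent.** Table 3-1 lists all cytogenetic categories for switchers, and section 10.5.2 tabulates the same categories on the whole FAS, baseline CCyR included. This stands: putting the full category table on the whole Switch Analysis Set is not a departure. But the randomised arms also get a restricted CCyR rate and shift tables, and no text available gives switchers either.
- **Time to CCyR may not be analysed.** With 20 switchers and p = 20%, expected CCyR events are 20 × 0.20 = 4.0 with k = 0, or 1 + 19 × 0.20 = 4.8 with k = 1. Both are below the threshold of 5. This stands, and it limits the point mainly to the rate.
- **The size is assumed.** This stands too. The documents give neither the number of switchers nor the number in CCyR at the switch.
- **The rule may be written elsewhere.** Only part of the document was available for review, and a separate analysis plan could hold it. However, section 10.6.1.1 does not defer to one for switchers, whereas section 10.6.2 does for exposure-response.

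Two stronger readings are tempting but not supported. A reader might infer that the criterion "At any time after the initiation of therapy, new clonal chromosome abnormalities in Ph+ cells: CCA/Ph" is another route to switching in CCyR. It is not: the abnormality is in Ph+ cells, CCyR means no Ph+ metaphases, and FISH is not accepted (7.2.1.2).

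A reader might also infer that time to CCyR for switchers would run from randomisation, because section 10.5.2 says "Time to CCyR is defined for patients in the Cytogenetic Responder Set as: date of first CCyR - date of randomization +1". That formula belongs to the Cytogenetic Responder Set, whereas the switch analysis has its own set and its own S-Week schedule. Counting from the first asciminib dose is the natural reading, and saying so is a clarification only.

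**Conclusion.** The point holds as a minor, optional improvement. As written, a CCyR gained on bosutinib and kept to S-Week 24 counts as asciminib efficacy in the post-switch CCyR rate, and no available rule prevents it. With 20 switchers and a CCyR rate of 0% to 50% in the others, each retained case adds 5.0 to 2.5 points. Both inputs are assumptions. The number of affected patients is unknown and may be zero, and a patient who loses CCyR before the visit pulls the rate the other way.

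A reader might infer that the trial's efficacy conclusions are biased. The documents do not support that: the analysis is exploratory and untested, and the Amendment 3 rationale keeps efficacy data collected after the switch out of the primary and secondary endpoints.

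**What to change.** In sections 10.1.6 and 10.6.1.1, add one sentence each. Post-switch CCyR rate, time to CCyR and duration of CCyR are reported only for Switch Analysis Set patients not in CCyR on the bosutinib end-of-treatment (S-Baseline) marrow. The full cytogenetic category table stays on the whole Switch Analysis Set, with a shift table from S-Baseline. As a clarification, state that time is counted from the first asciminib dose.

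No new sample is needed. Section 7.2.1.2 schedules marrow on treatment "as long as patient has not achieved MMR and at end of treatment", and Table 7-1 shows it at the end-of-treatment visit. The rule copies the one that the sponsor already applies to the randomised arms. The cost is a smaller denominator, a less precise estimate and possibly a lower reported rate. The sentence should also say how a switcher without an evaluable end-of-treatment marrow is classed.
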